### 6.2. Preparation/Handling/Storage/Accountability

The Investigator or designee must confirm appropriate temperature conditions have been maintained during transit for all study intervention received and any discrepancies are reported and resolved before use of the study intervention.

- Only participants enrolled in the study may receive study intervention and only authorized site staff may supply or administer study intervention. All study interventions must be stored in a secure, environmentally controlled, and monitored (manual or automated) area in accordance with the labeled storage conditions with access limited to the investigator and authorized site staff.
- Capsules should be kept in their primary packaging until dispensing into participant dosing bottles.
- Monodose RS01 devices will be supplied in bulk. After use, the devices will be placed in a plastic bag, and the bag will be labelled with the participant number, day of dosing, and date. Devices will be disposed of at site after reconciliation is verified by Study Monitor.
- The Investigator, institution, or the head of the medical institution (where applicable) is responsible for study intervention accountability, reconciliation, and record maintenance (i.e., receipt, reconciliation, and final disposition records).
- Further guidance and information for the final disposition of unused study intervention are provided in the SRM.
- Under normal conditions of handling and administration, study intervention is not expected to pose significant safety risks to site staff. Take adequate precautions to avoid direct eye or skin contact and the generation of aerosols or mists. In the case of unintentional occupational exposure notify the Monitor, Medical Monitor and/or GSK Study Delivery Lead.
- A Safety Data Sheet (SDS)/equivalent document describing occupational hazards and recommended handling precautions either will be provided to the investigator, where this is required by local laws, or is available upon request from GSK.
- Precaution will be taken to avoid direct contact with the study intervention. A Safety Data Sheet (SDS) describing occupational hazards and recommended handling precautions will be provided to the investigator. In the case of

unintentional occupational exposure notify the monitor, Medical Monitor and/or GSK study contact.

### **6.2.1. Dosing Procedure**

Please refer to the SRM for dosing procedure.

### **6.2.2. Treatment Compliance**

Full details of treatment compliance will be provided in the SRM.

## **6.3. Measures to Minimize Bias: Randomization and Blinding**

All participants will be randomized, according to the randomization schedule generated prior to the study by the Biostatistics Department at GSK. Each participant will be dispensed blinded study intervention, labelled with his/her unique randomisation number, throughout the study. Each participant scheduled to receive study drug will receive a treatment allocation number when randomized. In Part A (Cohorts 1 and 2), Part B (Cohorts 3 and 4) and Part C (Cohort 5) participants will be randomized in a 3:1 ratio to receive study treatment (active drug: placebo).

This will be a double-blind study with participants and the site staff blinded. The site pharmacy will be unblinded. For dose escalation, the Sponsor study team physicians, statisticians, clinical safety and clinical pharmacokinetic staff and/or their delegates will have access to unblinded data, if necessary. Other Sponsor staff will remain blinded unless unblinding becomes necessary.

Once each cohort is complete, selected members of the sponsor staff may have access to unblinded PK and safety data for the given cohort, to enable the PK analysis and modelling and to support the planning of future studies.

The blind may be broken if, in the opinion of the Investigator, it is in the participant's best interest for the investigator to know the study treatment assignment. The Sponsor study team must be notified before the blind is broken unless identification of the study treatment is required for a medical emergency in which the knowledge of the specific blinded study treatment will affect the immediate management of the participant's condition. In this case, the Sponsor study team must be notified within 24 hours after breaking the blind. The date and reason that the blind was broken must be recorded in the source documentation and eCRF, as applicable.

Unblinded monitors, and in the event of a Quality Assurance audit, the auditor(s), will be allowed access to un-blinded study treatment records at the site to verify that randomization/dispensing has been done accurately.

A participant will be withdrawn if the participant's treatment code is unblinded by the Investigator or treating physician. The primary reason for discontinuation (the event or condition which led to the unblinding) will be recorded in the eCRF.

GSK's Global Clinical Safety and Pharmacovigilance (GCSP) staff may unblind the intervention assignment for any participant with an SAE. If the SAE requires that an expedited regulatory report be sent to one or more regulatory agencies, a copy of the report, identifying the participant's intervention assignment, may be sent to investigators in accordance with local regulations and/or GSK policy.

## 6.4. Study Intervention Compliance

- When the individual dose for a participant is prepared from a bulk supply, the preparation of the dose will be confirmed by a second member of the study site staff.
- When participants are dosed at the site, they will receive study intervention directly from the Investigator or designee, under medical supervision. The date and time of each dose administered in the clinic will be recorded in the source documents. The dose of study intervention and study participant identification will be confirmed at the time of dosing by a member of the study site staff other than the person administering the study intervention.
- A record of the quantity of GSK3923868 dispensed to and administered to each participant must be maintained and reconciled with study intervention and compliance records. Intervention start and stop dates, including dates for intervention delays and/or dose reductions will also be recorded.

## 6.5. Dose Modification

As this is a first time in human study, doses may be modified on the basis of emerging safety, tolerability and PK data. The dose escalation committee (DEC) will be responsible for dose selection and/or modification. See Section 10.1.5 for more information on the committee structure.

Specific PK criteria are outlined in Section 6.5.1 and dose escalation stopping criteria are outlined in Section 6.5.2.

### 6.5.1. Pharmacokinetic Criteria for Dose Modification

This protocol allows some alteration from the currently outlined dosing schedule, however in this study the maximum total daily dose will not exceed 3000 µg GSK3923868 and the maximum daily exposure of GSK3923868 is not intended to exceed the gender averaged steady-state exposure at the NOAEL in the 4-week rat intravenous toxicology study ( $AUC_{(0-24h)}$  593 ng.h/mL;  $C_{max}$  575 ng/mL). See Section 4.3 for further details.

The following dose modification and PK stopping criteria will be used:

- If exposure in a participant is predicted to reach 593 ng.h/mL for  $AUC_{(0-24h)}$  and/or 575 ng/mL for  $C_{max}$ , the dose for next cohort will be modified.
- If exposure in a participant reaches 593 ng.h/mL for  $AUC_{(0-24h)}$  and/or 575 ng/mL for  $C_{max}$ , the dose escalation will be paused, and no further participants will be dosed at that level or at any higher dose level.

### 6.5.2. Dose Escalation Stopping Criteria

Further dosing at the current dose level stops and that dose and no higher dose may be used if any of the following occur:

- Any one participant experiences a serious adverse event that is considered at least possibly related to the study drug.
- Two participants experience a severe adverse event or bronchospasm that is considered at least possibly related to the study drug.
- Three participants meet liver chemistry stopping criteria outlined in Section [7.2.3](#).
- Three participants meet QTc stopping criteria outlined in Section [7.2.4](#).
- Three participants meet spirometry stopping criteria outlined in Section [7.2.5](#).
- Three participants experience any adverse event considered clinically important by the Investigator.

### 6.6. Treatment of Overdose

For this study, any dose of GSK3923868 greater than the planned nominal dose for the treatment period or cohort within a 24-hour time period up to minus 1 hour will be considered an overdose.

GSK does not recommend specific treatment for an overdose. The Investigator (or physician in charge of the participant at the time) will use clinical judgement to treat any overdose.

In the event of an overdose, the Investigator (or the treating physician) should:

1. Contact the Medical Monitor immediately.
2. Closely monitor the participant for AE/SAE and laboratory abnormalities for 24 hours.
3. Obtain a plasma sample for PK if requested by the Medical Monitor (determined on a case-by-case basis).
4. Document the quantity of the excess dose as well as the duration of the overdosing in the CRF.

Decisions regarding dose interruptions or modifications will be made by the Investigator in consultation with the Medical Monitor based on the clinical evaluation of the participant.

### 6.7. Concomitant Therapy

Any medication or vaccine (including over the counter or prescription medicines, recreational drugs, vitamins, and/or herbal supplements) or other specific categories of interest that the participant is receiving at the time of enrolment or receives during the study must be recorded along with:

- Reason for use

- Dates of administration including start and end dates
- Dosage information including dose and frequency

The Medical Monitor should be contacted if there are any questions regarding the acceptability of concomitant or prior therapy.

Participants must abstain from taking prescription or non-prescription drugs (including vitamins, recreational drugs, and dietary or herbal supplements) within 7 days before the first dose of study intervention until completion of the follow-up visit, unless, in the opinion of the Investigator and Medical Monitor, the medication will not interfere with the study procedures or compromise participant safety.

Paracetamol/Acetaminophen, at doses of  $\leq$  2 grams/day, and/or use of simple analgesics is permitted for use any time during the study. Other concomitant medication may be considered on a case-by-case basis by the Investigator in consultation with the Medical Monitor.

In Part C, depending on asthma severity participants will also be permitted to use SABA, ICS, ICS/LABA or LTRA to control their asthma.

GSK3923868 is not expected to perpetrate a drug-drug interaction (DDI) on the pharmacokinetics of these therapies; GSK3923868 is considered to pose a low risk of a systemic DDI with substrates of CYP3A4, OATP1B1 or MATE1. Montelukast is metabolised by CYP2C8. Currently there is no information on whether GSK3923868 is an inhibitor of CYP2C8, however, from the montelukast SPC coadministration of gemfibrozil (a strong CYP2C8 inhibitor) with montelukast (a sensitive CYP2C8 substrate) does not result in a clinically relevant DDI and dose adjustment is not recommended.

GSK3923868 is not expected to be a victim to a DDI with these therapies as they are not clinically relevant inhibitors/inducers of CYP450 or inhibitors of drug transporters.

### **6.7.1.      Rescue Medicine**

For asthmatics in Part C of this study SABA (e.g. salbutamol) will be permitted to be used as rescue medication. This will be provided by the participant or, if necessary, supplied by the study site.

The use of rescue medications is allowable and at any time during the study. The date and time of rescue medication administration as well as the name and dosage regimen of the rescue medication must be recorded.

## 7. DISCONTINUATION OF STUDY INTERVENTION AND PARTICIPANT DISCONTINUATION/WITHDRAWAL

### 7.1. Discontinuation of Study Intervention

In rare instances, it may be necessary for a participant to permanently discontinue study intervention. If study intervention is permanently discontinued, the participant will be withdrawn from the study and will be asked to complete study discharge procedures as described listed in Section [7.3](#).

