### 2.3.1. Risk Assessment

Potential Risk of Clinical Significance	Summary of Data/Rationale for Risk	Mitigation Strategy
Study Intervention [GSK3923868]		
Bronchospasm	Can potentially occur with any inhaled treatment.	
Inclusion/Exclusion criteria: In Parts A and B healthy participants with an FEV1 and an FVC < 80% of predicted normal value will be excluded. In Part C only participants with mild to moderate asthmatics with a pre-bronchodilator FEV1 > 65% of predicted normal value will be recruited.
 
Monitoring: All doses of study treatment will be administered in the clinical pharmacology unit in the presence of clinical staff. Spirometry will be conducted pre and post dose to monitor participants.
 
Management: Treatment with a short-acting inhaled bronchodilator will be available. If bronchospasm occurs GSK3923868 will be discontinued immediately. The participant will be assessed and, if necessary, further therapy will be given as deemed appropriate by the Investigator or the attending physician.
 
Participants will be withdrawn from the study if bronchospasm occurs.

Respiratory tract irritancy	In rats dosed for 4 weeks by inhaled administration, microscopic findings were noted in the lungs and bronchi, with minimal degeneration/regeneration of the epithelium at	Appropriate safety margin: Maximum clinical exposure at 3 mg are expected to be below the

Potential Risk of Clinical Significance	Summary of Data/Rationale for Risk	Mitigation Strategy

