### 7.2.5. Spirometry Stopping Criteria

Any participant experiencing a reduction in FEV1 at the 1-hour post-dose time point compared to daily predose value of > 25% in Parts A and B and > 20% in Part C will be withdrawn from the study.

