### 7.2.7. Temporary Discontinuation

Participant withdrawn from the study treatment will be withdrawn from the study.

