## 7.3. Participant Discontinuation/Withdrawal from the Study

- A participant may withdraw from the study at any time at his/her own request or may be withdrawn at any time at the discretion of the investigator for safety, behavioural, or compliance reasons. This is expected to be uncommon.
- At the time of discontinuing from the study, if possible, the procedures outlined in the SOA on the day of discharge from the clinical unit should be completed (i.e. Days 2, 3, 18 and 8 for Parts A Cohort 1, A Cohort 2, B and C respectively).
- The participant will be permanently discontinued both from the study intervention and from the study at that time.
- If the participant withdraws consent for disclosure of future information, the Sponsor may retain and continue to use any data collected before such a withdrawal of consent.
- If a participant withdraws from the study, he/she may request destruction of any samples taken and not tested, and the Investigator must document this in the site study records.
- If participants prematurely discontinue in the study, they may be replaced at the discretion of the Medical Monitor in consultation with the Principal Investigator.

In Part A, the replacement participant will be assigned to the same treatment sequence and may start the treatment period where the last participant prematurely discontinued. In Parts B and C participants will be assigned to same treatment as the participant prematurely discontinued.

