#### **7.5. Management of Participants who Develop COVID-19 Symptoms During the Study**

If a participant develops COVID-19 like symptoms during the course of the study the following actions should be taken:

- During Part A (SAD portion of the study), when in the Unit participants who develop a high clinical index of suspicion for COVID-19 disease should be isolated and tested for COVID-19 in accordance with site procedures. Participants who develop symptoms suspicious of COVID-19 during washout periods should inform the site immediately.
- During Part B and C (Repeat dose of the study in HV and asthma patients), study treatment should be halted for any participants who develop a high clinical index of suspicion for COVID-19 disease; they should be isolated and tested for COVID-19 in accordance with site procedures.
- In all cases, for participants who are in the Unit, assessments should be continued as per the protocol during this period. Participants with a confirmed COVID-19 test may continue to complete safety monitoring assessments but will receive no further

doses of the study treatment. In other cases, withdrawal of participants from the study will be at the discretion of the Principal Investigator and discussed with the GSK Medical Monitor if required.

- Refer to [Appendix 8](#) for further COVID-19 related study management details.

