### **8.2.1. Time Period and Frequency for Collecting AE and SAE Information**

- All SAEs will be collected from the start of screening until the follow-up visit at the time points specified in the SoA (Section 1.3).
- All AEs will be collected from the start of intervention until the follow-up visit at the time points specified in the SoA (Section 1.3).
- Medical occurrences that begin before the start of study intervention but after obtaining informed consent will be recorded as Medical History/Current Medical Conditions not as AEs.
- All SAEs will be recorded and reported to the Sponsor or designee immediately and under no circumstance should this exceed 24 hours, as indicated in [Appendix 3](#). The investigator will submit any updated SAE data to the sponsor within 24 hours of it being available.
- Investigators are not obligated to actively seek information on AEs or SAEs after the conclusion of the study participation. However, if the investigator learns of any SAE, including a death, at any time after a participant has been discharged from the study, and he/she considers the event to be reasonably related to the study intervention or study participation, the Investigator must promptly notify the Sponsor.

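### Stopping study drug ends study participation without requiring the 7 to 14 day adverse-event call, so later new AEs can be missed in participants stopped for toxicity

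*Protocol*

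**What the plan says.** Three protocol sections tie the end of dosing to the end of participation.

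- Section 7.1: "If study intervention is permanently discontinued, the participant will be withdrawn from the study".
- Section 7.2.7: "Participant withdrawn from the study treatment will be withdrawn from the study".
- Section 7.3: "The participant will be permanently discontinued both from the study intervention and from the study at that time".

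Section 7.3 also sets out what is done on leaving: "At the time of discontinuing from the study, if possible, the procedures outlined in the SOA on the day of discharge" are to be completed. The follow-up call is not mentioned.

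Several safety triggers lead straight to study withdrawal. Section 2.3.1 says: "Participants will be withdrawn from the study if bronchospasm occurs". Section 7.2.5 says that a participant with a 1-hour post-dose FEV1 reduction "compared to daily predose value of > 25% in Parts A and B and > 20% in Part C will be withdrawn from the study". Section 7.2.6 does the same for an asthma exacerbation in Part C.

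On data collection, Section 8.2.1 says: "All AEs will be collected from the start of intervention until the follow-up visit". The Schedule of Activities makes that follow-up a telephone contact 7 to 14 days after the last dose, covering AEs, SAEs and concomitant medication. Section 8.2.1 also relieves investigators of any duty to go looking for AEs or SAEs once a person's participation has concluded.

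AEs and SAEs are primary endpoints in all three parts. The SAP (Sections 3 and 4.2.2.1) analyses everyone who took at least one dose and reports AEs as counts and percentages. The SAP text gives no rule for unequal follow-up.

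**The concern.** Leaving observation is linked to the outcome. The participants who stop drug because of a respiratory or liver event are those whose later course says most about tolerability, and they have the shortest required AE follow-up. A completer is asked about AEs 7 to 14 days after the last dose. After the discharge procedures, no section requires that contact for a participant stopped for toxicity.

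The Safety set keeps that participant in the denominator. A second AE that starts after departure may never reach the numerator. The error therefore runs one way, towards a better apparent safety profile. Groups are small (12 active in each of Parts B and C), and the escalation rules in Section 6.5.2 act on counts of one to three participants, so one unrecorded event is not negligible.

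The protocol is also not uniform on whether a person can be off drug but on study, so sites could reasonably act differently.

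**Working it through.** **Step 1. How each event leads out of the study, and what must still be done.**

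| Event | Route | Required afterwards, beyond discharge-day procedures |
|---|---|---|
| Bronchospasm | 2.3.1, direct withdrawal | No scheduled AE contact |
| FEV1 fall | 7.2.5, direct withdrawal | No scheduled AE contact |
| Asthma exacerbation | 7.2.6, direct withdrawal | No scheduled AE contact |
| Liver stopping event | 7.2.3 stops drug; 7.1 then withdraws | Liver monitoring to resolution or stabilisation (Appendix 5); no scheduled AE contact |
| QTc criterion | 7.2.4: withdrawal from drug is considered; its note then speaks of withdrawal from the study | Depends on the decision taken |
| Confirmed COVID-19 | 7.5: "Participants with a confirmed COVID-19 test may continue to complete safety monitoring assessments but will receive no further" doses | Safety monitoring is allowed |
| Pregnancy | 8.2.5: drug stop and study withdrawal given as alternatives | Pregnancy follow-up |

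Sections 7.2.4, 7.5 and 8.2.5 allow for stopping drug without leaving the study. Sections 7.1, 7.2.7 and 7.3 do not. Section 8.2.7.2 extends follow-up of device deficiencies to people who have discontinued; no equivalent sentence covers new AEs.

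**Step 2. Required AE observation after the last dose.**

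- Part B completer: last dose Day 14, so the call falls on Day 14 + 7 = 21 to Day 14 + 14 = 28.
- Part C completer: last dose Day 7, so the call falls on Day 14 to Day 21.
- Participant stopped after the Day 3 dose in either part: the call, if required, would fall on Day 3 + 7 = 10 to Day 3 + 14 = 17.

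Measured from the last dose, a completer has 7 to 14 days of planned AE follow-up. A withdrawn participant has none required beyond the discharge procedures.

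**Step 3. Reproduce the plan's figures (Protocol Section 9.2, SAP Section 5).** The chance of seeing no event in n participants at true rate p is (1 − p)^n.

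| n | p = 5% | p = 20% | Plan states |
|---|---|---|---|
| 5 | 0.95^5 = 0.774 | 0.80^5 = 0.328 | 77%, 33% |
| 9 | 0.95^9 = 0.630 | 0.80^9 = 0.134 | 63%, 13% |
| 12 | 0.95^12 = 0.540 | 0.80^12 = 0.069 | 54%, 7% |

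All six agree. Each takes all n participants as observed for the event.

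**Step 4. Later-onset events when k of 12 are unobserved.** The documents give no discontinuation rate, so k = 1 to 3 is an assumption. The formula becomes (1 − p)^(12 − k), with no replacement.

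| k | p = 5% | p = 20% |
|---|---|---|
| 0 | 54% | 7% |
| 1 | 0.95^11 = 57% | 0.80^11 = 9% |
| 2 | 0.95^10 = 60% | 0.80^10 = 11% |
| 3 | 0.95^9 = 63% | 0.80^9 = 13% |

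**Step 5. Direction of the error in the AE table.** With 12 in the denominator and 12 − k observed, the expected reported proportion for a later-onset event is p × (12 − k)/12. At p = 20% this is 20% × 11/12 = 18.3% for k = 1 and 20% × 9/12 = 15.0% for k = 3.

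Steps 4 and 5 treat early departure as unrelated to the risk of a later event. If those stopped for toxicity carry a higher risk, the under-count is larger.

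**The case against.** The strongest reply is that the event that matters is already recorded. A participant stopped for toxicity is in the Safety set, the triggering AE is counted, and AEs leading to withdrawal have their own summary. Each participant counts once, at maximum severity or strongest relationship, so a further AE may not change the top-line table. This stands, and it limits the loss to new events after departure.

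Follow-up of known problems also continues. Section 8.2.3 follows SAEs to resolution and asks for proactive follow-up of reported AEs at later contacts. Section 8.1.5 repeats clinically significant laboratory tests. Appendix 5 monitors liver events, and Appendix 3 provides for further evaluation of AEs. This stands too, but these provisions mainly pursue events already found. They do not set a contact at which a withdrawn participant is asked about new ones.

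The protocol expects discontinuation to be rare, tests no hypothesis and does not forbid the call. Section 7.5 can be read as a deliberate COVID-19 exception rather than a contradiction. Section 8.2.1 could be read as covering withdrawn participants, since it names no exception. These points lower the stakes, but they do not supply a requirement: the sentence in 8.2.1 that ends active AE seeking with participation, taken with the immediate withdrawal in 7.3, leaves the call optional at best.

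A reader might infer that replacement removes the withdrawn participant from the analysis. The Safety set definition does not support that. A replacement adds a participant; the withdrawn one stays.

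**Conclusion.** The point holds in a limited form. The rule ends participation when drug stops, and no section then requires the AE/SAE call, so new AEs after departure can be missed in participants stopped for toxicity. The effect is an under-count with an unchanged denominator.

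Its size cannot be fixed from the documents. For 1 to 3 of 12 unobserved, the chance of seeing no later event is 57–63% against the plan's 54% at a true rate of 5%, and 9–13% against 7% at 20%. These figures assume no replacement and departure unrelated to later risk. They apply only to events starting after departure.

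Four stronger readings are tempting and not supported:

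- **One withdrawal costs 8% of the active group's follow-up (1/12 = 8.3%), or 17 days in Part B (Day 18 − Day 1).** The first assumes the participant contributes nothing; the second is the extreme of a Day 1 stop. Data up to departure are kept, and the call is timed from the last dose.
- **Late drug effects fall in the lost window because predicted target engagement takes about seven days to drop below 10%.** Protocol Section 4.3.1 gives that prediction for single doses, and nothing there links residual engagement to late toxicity.
- **A QTc finding forces departure.** Section 7.2.4 says only that withdrawal is considered.
- **Requiring the call would complete the primary endpoint.** It yields AE and SAE information only.

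**What to change.** State in the protocol that participants who stop study drug for any reason other than withdrawn consent to follow-up remain in the study for safety data collection. This would comprise the discharge-day assessments and the AE/SAE call 7 to 14 days after their own last dose. Then reconcile Sections 7.1, 7.2.7 and 7.3 with 7.2.4, 7.5, 8.2.1 and 8.2.5, so that stopping drug and leaving the study are separate events throughout.

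No rule on when or why dosing stops needs to change. The Safety set definition already keeps these participants, and discharge-day procedures are already requested, so the new element is mainly an explicit requirement for an existing contact.

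The cost is protocol wording and one telephone call per discontinued participant. The limit should be stated openly: scheduled ECG, laboratory and spirometry assessments after withdrawal are not restored.
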